## 9. Outcome Measures

[During COVID-19 health crisis, outcomes assessments will be completed via phone; abbreviated measures of cognition, and no measures of physical function will be obtained due to the limitations of phone administration. Blood samples will not be collected.]

**Cognitive Outcome Measures:** The Repeatable Battery for the Assessment of Neuropsychological Status (RBANS) total index score will provide the primary outcome for the trial. Secondary outcomes will be assessed using individual neuropsychological tests of processing speed, executive control, and new learning ability as follows: Trail Making Test Parts A and B (seconds to complete), and Stroop Color and Word Test (interference trial). These measures sample major domains of cognition affected in ICU survivors.

**Physical Performance and Cardiovascular fitness:** Physical training effects on balance and strength will be assessed via the Short Physical Performance Battery (SPPB), a validated objective assessment. The SPPB yields a performance score of 0-12 (0-4 poor, 5-7 intermediate, 8-12 good). A difference of 1 point indicates a significant change in function. Physical training effects on cardiovascular fitness will be assessed via the 2-minute step test. We have selected the 2-minute step test for cardiovascular fitness because it is a validated measure of aerobic capacity, does not require equipment, and can be used in the home setting. Grip strength with dominant hand will also be measured.

**Self-reported Mood and Anxiety symptoms:** We will use the Patient Health Questionnaire–9 (PHQ-9) and Generalized Anxiety Disorder Scale (GAD-7) to determine the impact of the intervention on ICU's survivors' mood and anxiety. The PHQ-9 is a nine-item depression scale with a total score from 0 to 27 and the GAD-7 is a seven-item anxiety scale with a total score from 0 to 21. Both of these scales are derived from the Patient Health Questionnaire, have good internal consistency, and test-retest reliability as well as convergent, construct, criterion, procedural and factorial validity for the diagnosis of major depression and general anxiety disorder.

**Self-reported quality of life outcomes:** ICU survivors' health-related quality of life will be assessed using the Medical Outcome Study Short Form (SF-36). This scale has eight components (physical functioning, role-physical, bodily pain, general health, vitality, social functioning, role-emotional, and mental health) that are aggregated into a Physical Component Summary (PCS) and a Mental Component Summary (MCS). We will use both the PCS and the MCS as the quality of life outcomes. Changes that differ between groups by 2 or more points on a scale of 0 to 100 have been shown to be clinically or socially meaningful.

**Collection of Biological samples:** The blood will be collected and stored according to biological samples protocol to maximize sample quality and decrease sample variability due to sample collection and processing techniques. Blood samples will be collected at baseline and at 3 months. The 3-month time-point is chosen because this marks the immediate post-training assessment phase, a point where we expect to see the maximum effect of interventions, improvements in the neurobiology and concomitant biomarker profile. Two tubes (one lavender- and one red- top) will be used to collect 20 ml of blood from each patient. These tubes will then be labeled with pre-printed labels with a de-identified code. To avoid biomarker degradation and platelet activation, these samples will be centrifuged immediately at 3000 x g. The supernatants will be removed and stored in aliquots so that multiple episodes of freezing and thawing will be unnecessary during assay procedures. An additional 4ml fresh blood will be collected at Baseline and/or 3 months for DNA extraction. The tubes will be placed on dry ice for transport. Once at the storage facility, the aliquots will be placed in pre-labeled boxes and the boxes stored at -80 °C.

**Biomarkers:** The conceptual model holds that the cognitive benefit of combined physical exercise and cognitive training is achieved through modulation of physiologic process (Secondary specific aim 2). As a result, we will measure circulating levels of the pro-inflammatory cytokines (IL-1, 6, 8, TNF- $\alpha$ ); the acute-phase reactant (CRP); neurotrophic factors (IGF-1, VEGF, BDNF); and markers of glial dysfunction and astrocyte activation (S-100 $\beta$ , GFAP). Serum marker quantifications will be performed in duplicates using pre-validated commercially available assay kits. Each kit employs 1-2 positive control(s) of known concentration and a negative control in every run. We will follow manufacturer provided established protocols for these assays.

**APOE Collection and Assay:** Genomic DNA will be extracted from blood samples using the DNeasy Blood & Tissue Kit (Qiagen, Inc., Valencia, CA) according to the manufacturer's protocol. Approximately 50ng of genomic DNA will be used for amplification. APOE genotypes will be determined by restriction enzyme digestion of amplified DNA.

**Plasma amyloid-β Aβ42/Aβ40:** As number of recent studies have reported that a low ratio of plasma amyloid-β Aβ42 over Aβ40 is associated with increased Alzheimer's disease risk and greater cognitive decline, we will explore the effect of a low ratio on our intervention. Samples will be analyzed using standard analysis techniques.

**Acute Health Care Utilization:** In addition to patient reported emergency department and hospital admission data, we will use the local data-warehouse to capture all of the data needed to determine utilization. Furthermore, we will also use the data from the Indiana Network for Patient Care (INPC) to complement any data use outside of our health system. INPC is the primary health information exchange in the state of Indiana and it provides data for acute care services from all of the health care systems within the state of Indiana. We will determine the number of emergency department visits and the number of re-hospitalizations during follow-up as well as the diagnoses associated with each utilization episode.

**Other data collection:** At hospital discharge and baseline we will measure subject's age, race, gender, years of education, visual acuity, height, weight, body mass index, heart rate, blood pressure, Charlson Comorbidity Index, APACHE II score, activities and instrumental activities of daily living (ADL/IADL) prior to ICU admission through Katz and Lawton scales, cognitive status prior to admission through IQCODE, cognitive and physical activity levels prior to admission, admission and discharge diagnoses, duration of mechanical ventilation, duration of delirium, ICU/hospital length of stay, and ICU and in-home medications. These measures will be used to describe the ICU survivors characteristics and as potential confounders.

Study team will request physical therapy, occupational therapy, and speech therapy records from rehab facilities to identify physical and cognitive training received between ICU discharge and study intervention for subjects discharged to a facility.

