**Secondary Specific Aim 1:** Separate mixed effects models will be used with repeated measures (SPPB, 2-minutes step, PHQ-9, GAD-7, SF-36 PCS and MCS) as the outcome variables, group, time and interactions between group and time as independent variables while adjusting for stratification variables and other baseline covariates that may be different among the four groups. Significant interactions between group and time in these models would indicate differences in changes of functional outcomes, depressive symptoms, and anxiety levels or quality of life over time among the four groups. Post-hoc analyses will also be conducted following significant interactions in the mixed effects models to compare the combined training group to the other three groups and to determine how early a group difference can be detected and whether the effect extends beyond the training period.

**Exploratory Aim 1:** Changes in the serum levels of CRP, IL-1, IL-6, IL-8, TNF-  $\alpha$ , S-100 $\beta$ , GFAP, BDNF, VEGF, and IGF-1 will be calculated and used as the dependent variables in ANCOVA models with group as the independent variable and adjusting for stratification variables and baseline covariates that are

found to be different among the groups in univariate comparisons. Post-hoc comparisons will be used following a significant group effect to compare biomarker levels in the combined training group to the other three groups.

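### The rule to spin both blood tubes immediately does not fit the serum assays specified for the biomarker panel, including BDNF and VEGF

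*Combined protocol and SAP*

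**What the plan says.** **Collection (Section 9, Collection of Biological samples).** The paragraph opens by deferring to a separate document: "The blood will be collected and stored according to biological samples protocol". It then specifies the draw: "Two tubes (one lavender- and one red- top) will be used to collect 20 ml of blood from each patient". The handling rule follows and makes no distinction between the tubes: "To avoid biomarker degradation and platelet activation, these samples will be centrifuged immediately at 3000 x g". What is kept is described only as follows: "The supernatants will be removed and stored in aliquots". Samples are taken at baseline and at 3 months.

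**Assay (Section 9, Biomarkers).** The target is described in these words: "we will measure circulating levels of the pro-inflammatory cytokines". The sentence goes on to list CRP, the neurotrophic factors (IGF-1, VEGF and BDNF) and the glial markers. The matrix is then named: "Serum marker quantifications will be performed in duplicates using pre-validated commercially available assay kits". Plasma is named only for the amyloid-beta ratio.

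**Analysis (Section 8, Exploratory Aim 1).** The dependent variables begin "Changes in the serum levels of CRP, IL-1, IL-6, IL-8", and the same list runs on to BDNF, VEGF and IGF-1. The changes are compared across the four groups by ANCOVA.

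**Power (Section 8, Sample Size and Power).** The plan states 81.7% power for an overall treatment effect on biomarker changes. It assumes 0.31 SD in each single-intervention arm and 0.62 SD in the combined arm, at alpha 0.05.

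**The concern.** The plan itself treats platelet activation as something that would harm these measurements, yet it names a matrix whose preparation involves platelet activation. Staff processing the red-top tube cannot follow both instructions, and the protocol does not say which one yields. Different staff, or the same staff at different visits, could resolve it differently.

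This matters most for BDNF and VEGF. It is general laboratory knowledge, not something stated in the documents, that platelets hold and release both. The outcome is a within-person change, so a difference in processing between the two draws enters it directly. The two draws may well differ in setting. Section 6 places the first in the hospital stay and allows it to be combined with clinical sampling or taken from indwelling catheters; the second, at 3 months, is taken by a phlebotomist. The data listed under Other data collection in Section 9 include neither platelet count nor processing time, so the plan does not provide for a later check or adjustment.

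At stake is how the mechanism result for two of the three neurotrophic markers can be read. If handling is not fixed, a null result could be hard to tell apart from handling noise.

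**Working it through.** **Step 1. The instructions side by side.**

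| Item | Source | What it requires |
|---|---|---|
| Tubes | Section 9, Collection | one lavender-top, one red-top |
| Spin | Section 9, Collection | immediate, for both, to avoid platelet activation |
| Clotting time | Section 9, Collection | none given |
| Stored fraction | Section 9, Collection | supernatant, not identified as serum or plasma |
| Matrix for BDNF and VEGF | Section 9, Biomarkers; Section 8, Exploratory Aim 1 | serum |
| Tube assigned to BDNF and VEGF | nowhere | none given |

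The red-top tube leaves two possibilities:

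- Spun at once: little or no clotting has taken place, so the supernatant is not properly serum. How far clotting has gone depends on the minutes between draw and spin.
- Left to clot and then spun: the supernatant is serum, but the spin was not immediate and platelets were activated.

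The lavender tube (EDTA, by the usual colour convention) can be spun at once without difficulty, but it yields plasma, which is not the matrix stated for the panel. No route meets every instruction as written.

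**Step 2. The plan's own power figure.** Take four groups with means 0, 0.31, 0.31 and 0.62 SD, 60 evaluable per group and alpha 0.05. The grand mean is 1.24/4 = 0.31. The noncentrality is 60 × (0.31² + 0 + 0 + 0.31²) = 60 × 0.1922 = 11.53, with 3 and 4 × 59 = 236 degrees of freedom. Power from the noncentral F distribution is 81.7%, which matches the plan. The power arithmetic is not in error.

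**Step 3. What extra noise could do, under an assumption.** Let q be the share of the variance of the measured change that comes from handling or platelet release unrelated to treatment. The documents give no value for q. Suppose also that the planned 0.31 and 0.62 SD refer to the circulating level free of that noise. Each effect is then multiplied by √(1 − q):

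| q (assumed) | Combined-arm effect (SD) | Power, 60 per group |
|---|---|---|
| 0 | 0.620 | 81.7% |
| 0.10 | 0.588 | 77.1% |
| 0.25 | 0.537 | 68.4% |
| 0.50 | 0.438 | 49.3% |
| 0.75 | 0.310 | 26.1% |

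If instead the planned SD is that of the change as actually measured, this noise is already in it and no deduction applies. The table shows why consistent handling is worth securing. It is not an estimate for this trial.

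**The case against.** The strongest reply is that handling detail is delegated. Section 9 cites a biological samples protocol intended to limit variability from collection and processing, and the kits are to be run by the manufacturers' procedures. Clotting time and tube assignment may well be set there. That document is not available here, so one cannot conclude that handling is uncontrolled in practice. This stands, but it does not remove the conflict: the protocol's own sentence sends both tubes to an immediate spin, and a separate document that does otherwise would contradict it.

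A reader might infer several stronger things that the documents do not support.

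- *That the BDNF and VEGF assays mainly read platelet release.* The documents neither say that platelets carry these markers nor give a share. A stable within-person platelet contribution would also cancel in a change score.
- *That the 81.7% power fails for these markers.* This needs a value for q and a reading of the planned SD that excludes handling noise. The plan supplies neither.
- *That the group comparison is biased.* Differences in handling between visits should fall on all randomised arms alike. Bias would require training itself to alter platelet number or reactivity, and nothing in the documents shows that.
- *That the two draws always differ in setting.* Section 4 allows the baseline assessment, when blood is taken, to be completed at home, and home collection at 3 months is only implied.
- *That every passage ties BDNF and VEGF to serum.* In Section 2, Exploratory Aim 1, the word is attached to the markers expected to fall and is not repeated for BDNF, VEGF and IGF-1. The point therefore rests on Sections 8 and 9.

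Serum also has a documented rationale: Section 2 says the programme builds on a repository of serum delirium biomarkers.

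**Conclusion.** The point holds as a conflict between a stated handling rule and the stated matrix. Followed literally, the immediate spin does not give serum from the red-top tube, and the protocol does not say how to resolve this. The conclusion rests on the text of Sections 8 and 9 and on the ordinary definition of serum.

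The consequence is a risk of unknown size: variable time to spin may add platelet-related noise to the change scores, particularly for BDNF and VEGF. That those two are especially exposed is general laboratory knowledge. The expected cost is precision and clarity of the mechanistic reading, not a demonstrated bias. Only the biomarker aim is touched. Section 2 and the analysis paragraph of Section 8 call it exploratory, although the power paragraph and the Biomarkers paragraph call it Secondary Aim 2. RBANS and the other clinical outcomes are unaffected.

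**What to change.** 1. In Section 9, Collection of Biological samples, apply the immediate spin to the lavender tube only.
2. In the same place, set one fixed clotting time before the red-top tube is spun, the same at baseline and at 3 months.
3. In Section 8 (Exploratory Aim 1) and in both Section 9 paragraphs, name the tube and matrix for each analyte.
4. Bring the biological samples protocol into line with this wording.
5. Record the draw-to-spin time for each tube at each visit.

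The cost is wording in the protocol and laboratory procedure, plus one recorded time per tube. No extra tube, blood volume or visit is needed. Samples already processed inconsistently cannot be repaired afterwards, so any processing times already held should be retrieved.

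Measuring BDNF and VEGF in plasma from the lavender tube is an option for the sponsor to weigh, not a required change. It avoids clotting, but it uses part of the plasma, needs kits validated for plasma, and gives up comparability with the programme's serum repository.

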## 10. Privacy/Confidentiality Issues

***Loss of confidentiality*** is a risk in this type of data collection. Our data management and quality assurance techniques have proven effective in past trials in maintaining confidentiality and all study personnel have completed training in Human Subjects Research and HIPAA standards.

## 11. Follow-up and Record Retention

This is a five-year study and study documents will be destroyed seven years after the end date of the study.

